## Blood and other Biological Samples

Please create or insert a table describing the proposed collection of blood or other biological specimens. A 20cc blood sample will be drawn at baseline. General medical tests will be performed, such as CBC, Chem 7, LFTs, TSH, cholesterol, B12, and folate.

## Assessment Instruments

Create a table or give a brief description of the instruments that will be used for assessment.

Cumulative Illness Rating Scale-Geriatric (CIRS-G) (71) will be filled out at baseline to measure chronic medical illness burden.

Psychiatric diagnosis and eligibility will be determined at screening using the Structured Clinical Interview Diagnostic for DSM 5 (SCID) (72) and MMSE.

24-item HRSD: standard measure of depression severity that measures changes in depressive symptoms.

CGI Severity and Improvement (73): scales measuring the clinician's view of subjects' global functioning that will provide a clinical assessment of subjects at each visit and help maintain safety by identifying clinical worsening.

Structured Pill Count Interview: assessment of study medication compliance accounting for each dose of prescribed study medication during the study period.

Treatment Emergent Side Effect Scale: standardized general checklist used in our clinic for monitoring side effects associated with medication treatment.

Inventory of Depressive Symptoms—Self Report (IDS-SR) (74): rating scale based on DSM criteria that is increasingly used in antidepressant studies due to its equivalent weightings for each item and understandable anchor points.

The Social Adjustment Scale Self-Report (SAS-SR) is a self-report scale that measures instrumental and expressive role performance over the past 2 weeks in adults (75). The 54-item assessment covers six areas of functioning, including work (either as a paid worker, unpaid homemaker, or student), social and leisure activities, relationships with extended family, role as a marital partner (if applicable), parental role (if applicable), and role within the family unit (including perceptions of economic functioning).

Blind assessment—Clinician and Patient Versions: rates clinician and participant's guess as to the identity of active vs. sham hearing aids.

Physical function will be assessed at baseline and Week 12 using the Short Physical Performance Battery (SPPB) (76), a performance measure of gait, balance, and lower extremity strength.

Patients' gait will be assessed by trained raters as walking speed in m/s on a Gaitrite walkway system. The Gaitrite walkway system is a portable, 27-foot long mat which measures temporal (timing) and spatial (distance) gait parameters (temporal/spatial) via grids of embedded, pressure-sensitive sensors connected to a computer.

The Repeatable Battery for the Assessment of Neuropsychological Status (RBANS) (78-79) was designed to reliably examine intelligence, attention, memory, language, and visuospatial/constructional ability (80-81). This RBANS for Hearing Impaired Populations (RBANS-H) will be employed in the current study, and all components of the RBANS-H the instructions in are presented in written format on an external computer monitor simultaneous with the oral administration.

Because the RBANS-H has relatively low coverage of executive functioning, we are supplementing it with measures from the NIH Toolbox (Dimensional Change Card Sort Test and the Flanker Inhibitory Control and Attention Test) (83).

Physical activity is assessed via a measure of weekly kilocalories (kcal) derived from the 18-item Minnesota Leisure Time Physical Activity Questionnaire (106), with activity levels < 383 kcal considered frail.

Please attach copies, unless standard instruments are used

## Off label and investigational use of drugs/devices

Choose from the following that will be applicable to your study

## Research Related Delay to Treatment

Will research procedures result in a delay to treatment?

Yes

Maximum duration of delay to any treatment

N=20 subjects will receive hearing aids that are not fully tuned such that they improve hearing, so there is a delay for hearing treatment. Mitigating this risk are the facts that all subjects will be offered an active treatment for depression (i.e., antidepressant medication), and all subjects will be aware that they will receive functioning hearing aids for their hearing loss at the end of the study. However it is possible that antidepressant and hearing treatment may be delayed due to scheduling study MRI scans and audiology visits, though we will make every effort not to delay treatment. If there are scheduling difficulties, treatment will not be delayed more than 1 week.

Maximum duration of delay to standard care or treatment of known efficacy

See above.

Treatment to be provided at the end of the study

As per study procedures, all subjects will receive free functioning hearing aids at the end of the study as well as 3 mo open treatment in LLDC.

## Clinical Treatment Alternatives

Clinical treatment alternatives

The alternative to participating in this study is to seek treatment outside the research project. Patients who would rather receive treatment elsewhere will be given referrals to appropriate and affordable care.

## Risks/Discomforts/Inconveniences

Risks that could be encountered during the study period

1. Interview, emergencies, and possible suicidal ideation: Subjects may experience discomfort during the clinical interview and evaluations when discussing symptoms and current life events. The study coordinators are experienced and skilled in interviewing depressed subjects. Half-way through the initial assessment, the coordinator will ask the subject if they would like to take a break, and this will be provided if desired. A study clinician will be available during all aspects of the assessment if there are any questions or problems. In addition, should the subject express suicidal ideation at any time during the interview, the study clinician will be contacted immediately to assess the subject and to determine the appropriate course of action. Options for addressing suicidal ideation will include contacting the individual's mental health caregiver, referring for urgent (same day) evaluation and treatment in an outpatient clinic, or emergency room evaluation and hospitalization. Similar practices will be used for other emergencies, including but not limited to psychosis, homicidal or violent thoughts, or an acute change in a subject's physical status.

2. Antidepressant Side Effects: Side effects will be assessed at each planned visit and if needed through additional or unscheduled contacts. We will attempt to minimize side effects by slow dosage titration and allowance for dose reduction if needed. We will withdraw subjects from the study if they cannot tolerate the lowest dose of escitalopram or duloxetine. Side effects of these medications include somnolence, diarrhea, nausea, impaired ejaculation, impotence, dry mouth, tremor, and sweating. Escitalopram and duloxetine have black box warnings regarding an increased risk for suicidal thinking and behavior in adolescents and young adults (less than 24 years old) given the drug. Both drugs are of unknown risk to a fetus. Since the proposed study will enroll subjects aged 60-90 years, these particular risks are not expected to be applicable. Regardless, all subjects will be asked to tell their doctors immediately if they experience suicidal thoughts, and menopausal status and date of last menstrual period will be documented in all female participants.

Subjects may be prescribed alternative medications (SSRI, SNRI, or bupropion) in the event they are judged to have failed or not tolerated escitalopram and duloxetine. As a class, SSRIs can be associated with somnolence, diarrhea, nausea, impaired ejaculation, impotence, dry mouth, tremor, and sweating, in addition to low risk of increased gastrointestinal bleeding in older adults. SNRIs as a class may be associated with these same risks, in addition to the risk of mildly elevated blood pressure at the upper dosage ranges. The most frequent (occurs in more than 25% of people) side effects of bupropion include

agitation, dry mouth, and headache. Common side effects (occurs in 1-25% of people) include excessive sweating, dizziness, tremor, constipation, nausea, decreased appetite, weight loss, rash, heart pounding, high blood pressure, unsteadiness when walking, confusion, anxiety, increased urination, and difficulty sleeping. Increased risk of seizures occurs in patients taking 400mgs or more.

3. Delay in Initiation of Hearing Treatment: A risk to subjects in this study is the potential delay in receiving effective treatment for their hearing loss. N=20 subjects will receive hearing aids that are not fully tuned such that they improve hearing. Mitigating this risk are the facts that all subjects will be offered an active treatment for depression (i.e., antidepressant medication), and all subjects will be aware that they will receive functioning hearing aids for their hearing loss at the end of the study.

4. Gait speed assessment: During the physical performance assessments, patients may feel unsteady and as such their risk of falls may increase. To mitigate these risks, patients are accompanied by research coordinators and/or doctors during each of the performance-based assessments (including the gait assessment, balance test, and chair stand, the latter two components of the Short Physical Performance Battery). Coordinators walk slightly behind and alongside the patients during the gait assessment, providing support for the patients should they become unsteady during the procedure.

5. Non-study antidepressant subgroup: A risk for those in this subgroup who do not wish to change their current antidepressant medication despite ongoing depressive symptoms is that their symptoms may not be adequately treated with an antidepressant medication. However, prior to assigning them to this subgroup, each subject will be counseled on the risks and benefits of antidepressant medication, will be offered to change antidepressant medications, and if they choose to not change antidepressant medication they will be closely monitored for clinical worsening throughout the study period. Prior to consenting the subject, we will also offer alternative treatments to participating in this study including psychotherapy outside of the research project. Furthermore, if the subject wishes to change antidepressant medications at any point during the study period they will be initiated on antidepressant medication under the guidance of the study clinician. Also mitigating this risk are the facts that all subjects will receive functional hearing aids for their hearing loss by the end of the study.

6) MRI risks: While there have been no reports of any harmful long-term effects caused by 3T magnets or magnets of even higher strength, the long-term effects of being placed in a magnet of this strength are unknown. Also, although there are no known risks associated with pregnancy, we will not scan someone who is pregnant. If the female subject is pre- or peri-menopausal, she will be asked to take a pregnancy test to ensure that she is not pregnant. Some people have reported sensations during MRI scans with the 3T magnet, such as "tingling" or "twitching" (or, very rarely, a painful sensation), which are caused by changes in the magnetic field. With any MRI scan, on occasion, some people experience nervousness or discomfort due to the scanner's small space and the need to lie still. Except for pacemakers, some types of metallic implants, and medication patches, we are not aware of any other potentially dangerous interactions or hazards associated with the MRI scan. The MRI scanner also produces a loud noise; earplugs will be provided to reduce this discomfort. If a subject experiences any discomfort and wish to stop the scan, they will be instructed to inform a MRI technologist, and he or she will stop the scan immediately.

7) COVID-19 Phase 1 Re-Opening: Due to the COVID-19, individuals are at increased risk for exposure to COVID-19 both in transit to NYSPI as well as during their time at NYSPI for in-person visits. Procedures

are in place to minimize this risk as well as minimize the number of in-person visits required for this protocol. Patients will be offered paid transportation (i.e. Uber car service) to clinic for in-person visits, subject to a \$50 limit each way per week, to help reduce potential exposure on public transportation. At NYSPI, personal protective equipment such as masks will be utilized at all times both by staff and participants, and social distancing will be adhered to when possible.

Describe procedures for minimizing risks

We have included our plans to minimize risk in our discussion of the risks themselves, please see above.

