### Overview

Following baseline evaluation and MRI scanning, each subject will be counseled on the role of antidepressant medications in clinically significant depressive disorders as well as the risks and benefits of starting/changing antidepressant medication. Subjects will be randomized to receive antidepressant medication (AD) in combination with either full amplification hearing aids or low amplification hearing aids. Subjects who do not wish to change their antidepressant medication will also be offered participation in a subgroup of the study and will be randomized to receive either full amplification hearing aids or low amplification hearing aids. Subjects, treating clinicians, and depressive/cognitive outcome assessors will be blinded to hearing aid assignment. At randomization (Week 0) subjects will have devices placed and receive education by an audiologist, who will not be blinded but will conduct identical procedures for full vs. low amplification hearing aids and will maintain the blinding with participants. Subjects will have follow up audiology appointments at Weeks 2, 6, and 12 to receive further education, monitor compliance, and ensure devices are working correctly. Failure to adhere to hearing aid use requirements at Weeks 2 and/or 6 (as determined by the usage data log), or any hearing aid complications will prompt an additional audiology appointment at Week 9. At Weeks 2, 4, 6, 9, and 12 subjects will complete depression follow-up visits. However, a weekly CGI severity score of 6 or 7 will prompt a weekly session to check-in with the subject.

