#### Antidepressant medication

1. Following baseline screening, subjects who choose to start a study medication will receive escitalopram 10mg per day or duloxetine 30mg per day. We opted to allow two potential medication choices so that study participation could be offered to individuals who had previously taken one medication and either not responded or not tolerated it. We selected escitalopram and duloxetine based on established efficacy in

MDD, favorable side effect profiles, minimal drug-drug interactions, and cost effectiveness (i.e., available as generics) (67-68).

2. If the best history-taking efforts of study staff (including patient interview, pharmacy records, or other medical records) indicate that a participant has not responded to or has not tolerated escitalopram or duloxetine, then we will offer an alternative SSRI, SNRI, or bupropion based upon our clinical assessment of the best option given the participant's other medications, medical health, and symptom profile. Similarly, if the patient either fails or is unable to tolerate both of the study medications during the study, they will be initiated on another medication that is clinically indicated. If this is the case, the subject receiving non-study AD medication will be responsible for the cost of the medication co-pay and will pick up the prescriptions from their pharmacy.

3. After 4 weeks if subjects do not meet remission criteria ( $HRSD \leq 10$ ), the dose of study medication will be increased to escitalopram 20mg or duloxetine 60mg for the remaining 8 weeks of the study. Similarly, the dose of the non-study antidepressant medication will be increased under the guidance of the study clinician. Subjects unable to tolerate an increased dose will have their medication reduced to the previously tolerated dose. If a study subject wishes to change antidepressant medication at any point during the study period they may do so under the guidance of the study clinician.

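### The protocol gives two conflicting rules for a participant who cannot tolerate the study antidepressants: withdrawal in the risk section, a switch of drug in the treatment section

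*Protocol*

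**What the plan says.** **The withdrawal rule.** Risks/Discomforts/Inconveniences, item 2 (antidepressant side effects): "We will withdraw subjects from the study if they cannot tolerate the lowest dose of escitalopram or duloxetine".

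**The switching rule.** Antidepressant medication, item 2, second sentence, covers a participant who turns out to be "unable to tolerate both of the study medications during the study, they will be initiated on another medication that is clinically indicated". Item 3 then puts dose increases of a non-study antidepressant in the study clinician's hands, alongside the week-4 step for the study drugs.

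**Related text on switching or on taking part without a drug change**
- Antidepressant medication, item 1, gives the reason for having two drugs: "study participation could be offered to individuals who had previously taken one medication and either not responded or not tolerated it".
- Item 2, first sentence, concerns a participant whose history shows that he or she "has not tolerated escitalopram or duloxetine, then we will offer an alternative SSRI, SNRI, or bupropion".
- Item 3: "If a study subject wishes to change antidepressant medication at any point during the study period they may do so".
- Risks, item 2, continued: "Subjects may be prescribed alternative medications (SSRI, SNRI, or bupropion) in the event they are judged to have failed or not tolerated" the two study drugs.
- Study Procedures, Overview: "Subjects who do not wish to change their antidepressant medication will also be offered participation in a subgroup of the study". Risks, item 5, says of the same people that "if they choose to not change antidepressant medication they will be closely monitored for clinical worsening throughout the study period".

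**Related text on withdrawal.** Criterion 4 of Criteria for Early Discontinuation withdraws a participant who has an adverse event or side effects of significant degree.

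**Analysis.** The SAP (Data Analysis) fits an ANCOVA to the change between Week 0 and Week 12.

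**The concern.** The same event, inability to take the study antidepressants, leads to exit in one section and to a new prescription in another. A site clinician cannot follow both.

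The withdrawal rule also fits the design poorly. Participants are randomised to full or low amplification, not to a drug. People who decline any antidepressant change are randomised and followed. People with known intolerance are admitted and given something else. It is hard to see what is gained by removing someone whose intolerance appears only after randomisation.

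What is at stake is the Week 12 value. A participant without one does not enter the SAP's change model. The protocol describes no assessment after withdrawal. That the value would be lost is therefore an inference, though a natural one. A non-completer must also return the hearing aids or buy them at $5,300 (Hearing aid procedures, item 3), so withdrawal may end exposure to the randomised treatment as well.

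**Working it through.** **Step 1. Is the conflict there on either reading of the word 'or'?**

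| Reading of the withdrawal sentence | Against item 2, second sentence | Result |
|---|---|---|
| Intolerant of both drugs | Same event, opposite outcome: new drug, dose managed by the study clinician | Direct contradiction |
| Intolerant of either drug | The participant leaves after the first drug, so nobody could become intolerant of both during the study | Item 2's provision for intolerance has no one to apply to |

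The conflict survives both readings.

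**Step 2. What the other sections add.**
- Item 3's freedom to change drug is worded as the participant's wish, not as a procedure for intolerance.
- Item 1 and the first sentence of item 2 concern history before entry.
- The continuation of Risks item 2 says alternatives may be prescribed; it does not say the person stays in.
- The Overview and Risks item 5 concern people who decline a change.

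All of these support switch-and-stay, but none directly contradicts the withdrawal sentence. Criterion 4 points the other way and partly agrees with it.

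**Step 3. The plan's own figure.** Description of Subject Population gives 40 enrolled and 32 completers. The allowance is 40 − 32 = 8, or 8/40 = 20%, and 32/(1 − 0.20) = 40. The 20% is inferred, so this is only a consistency check. The documents give no alpha, power, effect size or SD, and no power figure can be reproduced.

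**Step 4. How many people?** Assumptions, none from the documents: M = 20 to 40 participants take a study drug, and r = 2% to 20% cannot tolerate the lowest dose of a given drug. Expected numbers for M = 20 and M = 40:

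| r | Either drug: M × r | Both, independent: M × r² | Both, half overlap: M × r × 0.5 |
|---|---|---|---|
| 2% | 0.4 to 0.8 | 0.008 to 0.016 | 0.2 to 0.4 |
| 5% | 1 to 2 | 0.05 to 0.1 | 0.5 to 1 |
| 10% | 2 to 4 | 0.2 to 0.4 | 1 to 2 |
| 15% | 3 to 6 | 0.45 to 0.9 | 1.5 to 3 |
| 20% | 4 to 8 | 0.8 to 1.6 | 2 to 4 |

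Half overlap means that half of those intolerant of one drug are also intolerant of the other. Giving an alternative to people with known prior intolerance would lower all of these figures.

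**Step 5. Effect on precision.** For two arms with a common SD, the standard error relative to 16 + 16 is sqrt[(1/n1 + 1/n2)/(2/16)]:
- 16 + 15: 1.017
- 15 + 15: 1.033
- 15 + 14: 1.051

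These apply only once all 8 allowed losses are used. Inside the allowance the completer target is still met. Going from 20 + 20 to 19 + 19, for example, raises the standard error by a factor of sqrt(20/19) = 1.026.

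**The case against.** The strongest reply has four parts.

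*The discontinuation criteria control, and the risk sentence only applies them.* Someone who cannot take even the lowest dose may well meet criterion 4. This stands in part: any fix must deal with that criterion and must not override a safety rule. It does not remove the conflict, because the treatment section handles intolerance of both drugs expressly, by switching.

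*Withdrawal has a rationale.* Aim 2 concerns augmentation of antidepressant treatment, and Hypothesis 2 compares the two amplification levels on top of an antidepressant. This has some force. It is weakened because a switched participant is still on an antidepressant, and because the protocol randomises a subgroup with no drug change at all.

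*Staff would follow the treatment section.* They probably would, since it is the detailed procedure. In that case the withdrawal sentence costs nobody.

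*The size is guesswork.* This stands. Every rate in Step 4 is assumed.

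A reader might also infer that the protocol contradicts itself at every place where switching or participation without a drug change is allowed. The documents do not support that. The direct contradiction is with one sentence, and the rest is context.

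**Conclusion.** The contradiction between the withdrawal sentence and the second sentence of Antidepressant medication, item 2, is certain on the text, and the protocol does not resolve it. Criterion 4 needs to be reconciled with both.

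The number affected cannot be derived. Under the assumptions above it runs from close to zero to 8, and it reaches the whole loss allowance only at the extreme: 40 study-drug takers, 20% intolerance and the either-drug reading. That it is probably small is a judgement. The cost is some precision if the risk section is followed, and none if the treatment section is.

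Two stronger readings are tempting. One is that post-randomisation withdrawal biases the comparison of arms. The drug is not randomised, participants and treating clinicians are blinded to amplification, and nothing in the documents suggests that intolerance would differ by arm. The other is that the rule endangers the sample size. Nothing in the documents shows that the 8-person allowance would be used up.

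Severity: minor.

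**What to change.** 1. Replace the withdrawal sentence in Risks item 2 with:

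> *A participant who does not tolerate the lowest dose of a study antidepressant will be switched to another antidepressant, as set out under Antidepressant medication, and will stay in the study with the assigned hearing aids, unless the study clinician judges that an early discontinuation criterion is met.*

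2. Add to criterion 4 of Criteria for Early Discontinuation that intolerance resolved by lowering the dose or switching the drug does not by itself require withdrawal. Without this, the new sentence and criterion 4 would pull against each other.

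3. For anyone withdrawn who has not withdrawn consent, collect the Week 12 HRSD and CGI by virtual visit. Analyse them in the randomised arm, and record whether and when the aids were returned or bought.

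The cost is two short text changes and a few extra virtual contacts. The Week 12 text under COVID-19 Phase 1 Re-Opening already allows the psychiatric part of that visit to be virtual. Some Week 12 values would be taken after the devices had been returned, and the analysis must say so.

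The SAP is written in the past tense. If follow-up has ended, the report should state which rule was applied and how many participants in each arm were withdrawn for drug intolerance.
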